1.0 Objectives / Specific Aims

The objective of this proposal is to determine if combining vibration with hand task practice is superior to hand task practice alone in an adequately powered study.

Aim 1: To determine clinical potential of vibration in improving hand functional recovery

Hypothesis: Improvement of hand motor function will be greater for the treatment than control.

Aim 2: To determine the effect of vibration on sensorimotor grip control and neural communication

Hypothesis: The treatment will enhance sensorimotor grip control via strengthened neural communication for hand grip, compared with control.

2.0 Background

Post-stroke hand impairment is highly prevalent, persistent, and difficult to treat. Hand impairment has a profound negative impact on functional ability and independence.^{1,2} One way to improve treatment efficacy is to augment therapy with peripheral sensory stimulation.³ Afferent input is a powerful driver of change in the motor cortex.⁴⁻⁶ Sensory stimulation in conjunction with therapy has been shown to improve motor outcomes more than therapy alone.³ While promising, most modalities of sensory stimulation interfere with natural hand tasks, because suprathreshold electrical stimulation causes tingling sensation^{7,8} irrelevant to tasks at hand, and wearing of a glove or a finger cap hampers dexterous finger movement and causes a sense of discomfort.^{9,10} Thus, most modalities of peripheral sensory stimulation are administered prior to therapy, requiring additional time commitment. These constraints make it difficult for patient adherence and implementation.¹¹

To address these practical limitations and fully leverage the potential therapeutic benefits of sensory stimulation, we have developed a new stimulation that is imperceptible random-frequency vibration applied to wrist skin via a watch. We determined the optimal stimulation parameters (location, intensity, and frequency) based on our experimental data^{12, 13} and literature.¹⁴⁻²⁵ The theoretical framework is that imperceptible random-frequency vibration stimulates mechanoreceptors in wrist skin and afferents,^{26,27} adds small random currents to neurons in the sensorimotor cortex, triggering coherent¹⁶ firing¹⁸ at the peak of inputs related to hand tasks, and consequently enhances neural communication^{15, 28} for hand tasks¹⁴ and functional recovery. Our pilot data support the theoretical framework by demonstrating that neuronal firing magnitude and coherence in the cortical sensorimotor network for hand tasks increased with vibration vs. without, as measured by electroencephalogram (EEG). In addition, preliminary efficacy has been demonstrated in two pilot studies. First, use of vibration during 2-wk task-practice therapy resulted in greater improvement in manual dexterity assessed by the Box and Block Test (BBT) than dose-matched therapy alone, which sustained at follow-up (19 days post intervention).²⁹ Second, use of vibration during 6-wk task-practice therapy resulted in greater mean improvement in movement time assessed by the Wolf Motor Function Test (WMFT) compared with 10-wk task-practice therapy³⁰ and 12-wk manual therapy³¹ alone both at post and follow-up evaluations.

3.0 Intervention to be studied

Intervention to be studied is standardized hand task practice therapy (1-2 hours/session, 3 sessions/week for 6 weeks) with a watch (Fig 1) worn on the paretic wrist only during the therapy sessions. The watch is equipped with a vibrator and will apply vibration for the treatment group, and no vibration for the control group during therapy. The treatment vibration signal is adjusted to be imperceptible to the participant.

The use of watch vibration for the purpose of improving hand function has not been approved by the FDA, but has been approved as a nonsignificant risk device under the IDE regulation by the FDA. Use of the vibration for this purpose was safe in our previous pilot trial.²⁹

**Fig 1**

4.0 Inclusion and Exclusion Criteria/ Study Population

Inclusion Criteria

- 18 years old or older
- At least 6 months post stroke
- Wolf Motor Function Test (WMFT) total average time >10 s and hand task average time <120 s

Exclusion Criteria

- Currently undergoing other upper limb therapy
- Change in spasticity medication or upper limb botulinum toxin injection within 3 months prior to or during enrollment
- Severe spasticity that limits participation in task practice therapy (e.g., Modified Ashworth Scale=4-5)
- Complete upper extremity deafferentation
- Comorbidity affecting the upper limb function such as orthopaedic conditions limiting motion, premorbid neurologic conditions, premorbid peripheral neuropathy, compromised skin integrity of the wrist due to burn or long-term use of blood thinners, or significant neurological symptoms from interview-based screen for new symptoms similar to stroke and its worsening and severity
- Language barrier or cognitive impairment that precludes following instructions and/or providing consent

People with contraindications to MRI and/or TMS will participate in the study, but not complete the MRI and/or TMS. Contraindications to MRI and TMS include: pregnancy, epilepsy, history of brain tumor, hardware in the skull or spine (e.g., coils, clips), implantable medical devices (e.g., pacemaker), metal in the body that is not compatible with MRI.

Screening: Eligibility will be determined based on the potential participant's verbal disclosure or standardized clinical assessments. To minimize travel and face-to-face contact, video screening may also be used using HIPAA-compliant video applications (e.g., Microsoft Teams).

Plan to include a diverse population: We will include chronic stroke survivors of all genders and all racial and/or ethnic groups, since stroke occurs in persons of all genders and all racial and/or ethnic backgrounds. We will not exclude people based on sex/gender, racial or ethnic group. Our goal is to construct a participant pool that matches post-stroke survivor distributions in South Carolina, based on the stroke prevalence data in each sex, racial and ethnic group together with the sex, racial and ethnic distribution of the population in South Carolina. Recruitment of diverse groups is possible, because the RESTORE stroke registry currently has 48% female, 42% African-American, and 1% Hispanic.

Children: Children under the age of 18 years will be excluded. The rationale for exclusion of children is that stroke predominantly occurs in adults, and stroke is very rare in children. Importantly, these rare cases may actually differ in their etiology from the subjects we propose to study.

5.0 Number of Subjects

A total of 76 subjects will be recruited to participate in this study.

6.0 Setting

All activities will be conducted in a Laboratory located on the Medical University of South Carolina campus.

7.0 Recruitment Methods

Subjects will be recruited through the MUSC Registry for Stroke Recovery that has information of 838 stroke survivors who have agreed to be contacted for research (RESTORE, approved MUSC IRB PRO# 37803, [name] PI). In addition, a chart review will be conducted for research purposes. Potentially eligible patients will be identified. We will submit a Research Data Request to obtain a recruitment report of MUSC patients who potentially meet eligibility criteria. The potentially eligible patients who have agreed to be contacted for future research by logging their MUSC Research Permissions preferences in MyChart will be contacted by phone, letter, or email and invited to participate. Other patients who did not update their MUSC Research Permissions in MyChart may also be cold-contacted by phone, letter, or email to be informed of the study if it is appropriate. We will not cold-contact any patients who have chosen to opt-out of receiving contact about research or who have met the maximum number of contact attempts at the time of recruitment. In addition to the registry, advertisement via internet (e.g., South Carolina Research Studies Directory) will be used.

8.0 Consent Process

Consent will be obtained by the study personnel. The consent process will take place in a private room when the potential participant comes to the laboratory on a scheduled time agreed upon between the study personnel and the participant. The content of the consent will be verbally explained to the participant and the participant will be asked to raise any questions and concerns. If the person requests a waiting period, then one will be given. If the person desires to consent immediately, then the person will provide consent immediately.

9.0 Study Design / Methods

Study design: The study design is a double-blinded randomized controlled study. Participants will undergo standardized hand task practice therapy (3 sessions/week for 6 weeks) with the watch worn on the paretic wrist. Participants will be randomized into two groups: The device will deliver vibration for the treatment group and no vibration for the control group during therapy. Half the participants will be in the treatment group, and half in the control group. Double blinding is possible since treatment vibration is imperceptible (i.e., subthreshold). Evaluation will be performed at baseline, after 2, 4, and 6 weeks of continuous task practices and at 1-month follow-up.

Schedule: Participation will last 2.5 months. Participants' involvement entails 18 visits for therapy (each lasting 1-2.5 hours, 3 sessions/week for 6 weeks) and 2 evaluation visits (evaluations at each time point divided into 2 visits to minimize fatigue) for each of the 3 time points (baseline, after therapy, and follow-up), along with one time only, 30-min MRI assessment, resulting in a total of 25 visits over 2.5 months. Each activity is described below.

Therapy: Participants will undergo a standardized hand task-practice therapy program. Upper limb tasks for activities of daily living that are of the participants' interests and are related to participants' goals will be chosen and practiced with repetitions, in the laboratory. The difficulty level of the tasks will be modified per participants' progress. To translate improved motor capacity to independence at home, the paretic hand use in daily tasks at home will be tracked and encouraged.

Evaluation: Each of the two evaluation visits will last approximately 2-5 hours. The following assessments will be performed across the two evaluation visits.

Upper limb function assessment: Clinical upper extremity function scores will be assessed using conventional clinical assessments used in occupational/physical therapy in which participants will be asked to move the affected hand and arm, grasp objects and perform prescribed tasks (e.g., lifting an object off the table, releasing the object into a bin) as quickly as possible or at a comfortable speed, upon cues. These tests

will be videotaped for scoring. Position sensors will also be placed on the participant's upper limb using tape and be recorded. Participants will also complete a patient-centered outcomes questionnaire regarding self-reported abilities for activities of daily living and perception of the intervention. In addition, participants will be instructed to wear accelerometers on both wrists using standard wrist straps for 3 days outside the lab.

Neural assessment: Evaluations using electroencephalogram (EEG), magnetic resonance imaging (MRI), and transcranial magnetic stimulation (TMS) will be performed. For the EEG assessment, participants will wear an EEG cap on their head. Gel will be applied to individual EEG electrodes with a blunt syringe that does not penetrate the skin. During the assessment, the participant will rest comfortably in a chair and either rest or grip with the fingers.

TMS is used to locate the 'hand knob' of individual subjects functionally (vs. anatomically). The hand knob is the area in the precentral gyrus in the primary motor cortex that gives monosynaptic input to the hand muscles. The functional hand knob will be located using TMS, since it may have migrated out of the precentral gyrus through post-stroke reorganization. The functional hand knob will be identified by the 'hotspot' for the hand intrinsic muscle (APB) found using TMS if subjects are safe for TMS. Participants will sit on a chair and rest. A TMS coil will be placed on top of the subject's head. The TMS coil location will be moved around slightly to find the hotspot that stimulates neurons with direct monosynaptic projections to the alpha motoneurons in the spinal cord for the hand muscle, as seen by the evoked potential recorded using electromyogram (EMG) immediately after TMS. To record this from the muscle, subjects will have the surface EMG electrodes on the hand skin. TMS is administered to locate the hotspot, not as a treatment.

Additionally, one MRI assessment will be performed only one time during enrollment. The scan will be 20 minutes in duration. The MRI assessment is to obtain the individual participant's brain anatomy to facilitate subject-specific localization of brain activity.

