10.0 Data Management

Recruitment: Recruitment projects are housed in REDCap. Only study personnel will have access to the REDCap database while actively enrolling for the study.

Analysis: The primary analysis will be a repeated measures ANOVA for each outcome. The dependent variables will be the change from baseline at the evaluation times. The primary independent variables are group, evaluation time, and their interaction. We will also include sex as a biological independent variable along with its interactions. If the group by time interaction is significant, we will examine if there is a group difference at 10 weeks using post-hoc tests.

Sample size justification: The clinically meaningful difference in time needed to complete a functional upper limb task is deemed to be 4 to 7 s. This study will be powered to detect difference at follow-up of at least 4s in movement time between the treatment and control groups. For the repeated measures design with a significance level of 0.017 (adjusted for multiple comparison), at least 80% power, and 4 time points, for a standard deviation (SD) of 5.1s and compound symmetry correlation of 0.92 (both based on our pilot study²⁹), sample size of 32/group will be adequate. Adjusting for 15% attrition, 38/group is planned (total n=76).

Confidentiality: All data except for the consent forms and HIPPA forms will be coded at the time of data recording. All electronic data will be stored in a password-protected research server that is accessible to study personnel only. Videos of the upper limb movement will be recorded such that we will avoid capturing the participant's face, while capturing the hand, arm, and object being gripped. All paper data with personally identifiable information including the consent forms and HIPPA forms will be stored in a key-locked cabinet in a key-locked room that is accessible to study personnel only. Other paper data without personally identifiable information including testing sheets documenting testing sequences and notes will also be stored in a cabinet in a key-locked room that is accessible to study personnel only.

Data sharing: Only de-identified coded data will be reported and/or shared with the public and other investigators

in publications, in ClinicalTrials.gov, or via data depository.

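### The primary model of change from baseline leaves out baseline WMFT time, and no allocation method that would limit imbalance in starting severity is described

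*Combined protocol and SAP*

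**What the plan says.** Section 9.0 (Study design) states "Participants will be randomized into two groups" and "Half the participants will be in the treatment group, and half in the control group". Nothing there or elsewhere describes sequence generation, blocking, stratification, minimisation or concealment.

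Section 10.0 (Analysis) specifies a repeated measures ANOVA for each outcome: "The dependent variables will be the change from baseline at the evaluation times". The terms are group, evaluation time and their interaction, and then "We will also include sex as a biological independent variable along with its interactions". No baseline value is listed as a covariate.

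Section 4.0 requires "Wolf Motor Function Test (WMFT) total average time >10 s and hand task average time <120 s", so a measure of starting severity is needed to establish eligibility. Section 2.0 treats movement time as a WMFT measure. I therefore take the movement time in the sample size paragraph to be WMFT time.

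**The concern.** Room to improve in movement time plausibly depends on how slow a participant is at the start. Subtracting baseline removes the direct difference between arms. It does not remove the dependence of change on the starting value. If one arm happens to start slower, part of the observed group difference in change reflects that start.

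Two tools deal with this: balancing severity when allocating, and putting baseline in the model. The documents describe neither. In a trial of 76, a visible baseline difference would leave readers unsure how to interpret either a positive or a null result. Variation that baseline could explain would also stay in the error term.

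**Working it through.** **The plan's own figure.** Inputs from section 10.0: difference 4 s, SD 5.1 s, compound-symmetry correlation 0.92, significance level 0.017 (taken as two-sided), "at least 80% power, and 4 time points".

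- SD of the mean of four measures: 5.1 × √((1 + 3 × 0.92)/4) = 4.945 s.
- n per group: 2 × [4.945 × (z for two-sided 0.017 + z for 80% power)/4]² = 31.85, so 32, with power 80.2%.
- Attrition: 32/0.85 = 37.6, so 38 per group and 76 in total.

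The stated sample size reproduces, and this point does not affect it.

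**Size of chance imbalance at baseline.** With 38 per arm and no balancing on severity:

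- SE of the standardised difference = √(2/38) = 0.229 SD.
- 95% range = ±1.96 × 0.229 = ±0.45 SD.
- Chance of 0.25 SD or more: 28%. Chance of more than 0.3 SD: 19%.

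**Effect on the group difference in change.** The documents do not say whether 5.1 s and 0.92 describe raw times or change scores, and they give no correlation between change and baseline. I therefore take two readings.

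*Reading A: raw times, with baseline included in the 0.92 correlation.* The slope of change on baseline is 0.92 − 1 = −0.08. The SD of change is 5.1 × √(2 × 0.08) = 2.04 s. The correlation of change with baseline is −0.08 × 5.1/2.04 = −0.2.

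*Reading B: 5.1 s is the SD of change.* The correlation r with baseline is unknown, and I assume a size of 0.3 to 0.5. The shift is r × imbalance in SD units × 5.1 s.

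| Reading | Shift at 0.45 SD imbalance | Share of 4 s | Variance removed by a baseline covariate (r²) |
|---|---|---|---|
| A | 0.08 × 0.45 × 5.1 = 0.18 s | 5% | 0.2² = 4% |
| B, r = 0.3 | 0.3 × 0.45 × 5.1 = 0.69 s | 17% | 9% |
| B, r = 0.5 | 0.5 × 0.45 × 5.1 = 1.15 s | 29% | 25% |

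**Sex, for comparison.** I assume 36 women of 76, because "the RESTORE stroke registry currently has 48% female" (0.48 × 76 = 36.5). Under a fixed 38/38 split, the hypergeometric chance of 22:14 women or worse is 10.7%, and of 21:15 or worse 25.1%. At 22:14 women (so 16:24 men), the variance of the sex-by-group term is proportional to 1/22 + 1/14 + 1/16 + 1/24 = 0.2211. With perfect balance it is 2/18 + 2/20 = 0.2111. The increase is 4.7%. Averaged over all possible splits, the cost is about 1.4%.

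**The case against.** The strongest case against is that 1:1 randomisation without strata, analysed on change from baseline, is valid. Chance imbalance causes no bias over repeated trials, and the nominal error rate already allows for it. This stands: the shifts above are conditional on an unlucky draw, taken at the edge of the 95% range. It also stands that material harm is not demonstrated. Under Reading A the shift is only 0.18 s, and the documents do not settle which reading applies. What remains is that the stated model leaves out a baseline value that a change score already requires, and including it gains precision under either reading.

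A reader might infer more than the documents support, in four ways:

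- *That randomisation is unstratified by decision.* The documents give the ratio and are silent on the method.
- *That entry severity runs from 10 to 120 s.* The 10 s floor is on total average time and the 120 s ceiling is on hand task average time. These are two different WMFT scores, and no single score has both limits. None of the arithmetic above uses them.
- *That the absence of sex strata materially weakens the sex-by-group term.* Sex is already modelled, and the average variance cost is about 1.4%. That term is weak because of sample size: even with a perfectly balanced 16 per cell, power for a 4 s sex-by-group difference is 22% (SE = 4.945 × √(4/16) = 2.47 s).
- *That stratifying would prevent imbalance for every outcome.* A two-level cut limits imbalance on that factor only. It leaves variation within strata and does not balance the baselines of other outcomes, such as EEG.

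**Conclusion.** The point holds as a modest improvement to the analysis. Neither the described allocation nor the stated model deals with starting severity beyond the change score. At the ±0.45 SD limit, the group difference would shift by about 0.2 s (Reading A) or 0.7 to 1.1 s (Reading B) against the 4 s target. Adjusting for baseline would cut variance by about 4%, or by 9 to 25%, respectively.

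These sizes rest on 38 per arm, on a linear relation between change and baseline, and, for Reading B, on an assumed correlation. The validity of the planned test and the sample size of 76 are not in question. The missing allocation method is a gap in description, and the documents do not show that the method itself is poor.

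**What to change.** **Main change, section 10.0 (Analysis).** Add each outcome's baseline value as a prespecified covariate in its primary model. For movement time this is baseline WMFT time, kept continuous. The outcome can stay as change from baseline, because with baseline in the model the group effect is the same for change as for the follow-up value. The cost is one sentence and one degree of freedom. No new assessment is needed and N stays at 76. It should be fixed before outcome data are seen by group.

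**Optional, section 9.0 (Study design).** State how the 1:1 sequence is generated and concealed. If stratification is wanted, use concealed blocked allocation with two levels of entry WMFT total average time, the cut set in advance, and keep that factor in the model. Two strata would average 38 participants each (76/2). The downside is slightly uneven totals if blocks end incomplete. Section 10.0 says only that REDCap houses recruitment, so whether it can also run the allocation needs confirming. Unlike the covariate, stratification cannot be added for participants already allocated.

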10.0 Data Management

Recruitment: Recruitment projects are housed in REDCap. Only study personnel will have access to the REDCap database while actively enrolling for the study.

Analysis: The primary analysis will be a repeated measures ANOVA for each outcome. The dependent variables will be the change from baseline at the evaluation times. The primary independent variables are group, evaluation time, and their interaction. We will also include sex as a biological independent variable along with its interactions. If the group by time interaction is significant, we will examine if there is a group difference at 10 weeks using post-hoc tests.

Sample size justification: The clinically meaningful difference in time needed to complete a functional upper limb task is deemed to be 4 to 7 s. This study will be powered to detect difference at follow-up of at least 4s in movement time between the treatment and control groups. For the repeated measures design with a significance level of 0.017 (adjusted for multiple comparison), at least 80% power, and 4 time points, for a standard deviation (SD) of 5.1s and compound symmetry correlation of 0.92 (both based on our pilot study²⁹), sample size of 32/group will be adequate. Adjusting for 15% attrition, 38/group is planned (total n=76).

Confidentiality: All data except for the consent forms and HIPPA forms will be coded at the time of data recording. All electronic data will be stored in a password-protected research server that is accessible to study personnel only. Videos of the upper limb movement will be recorded such that we will avoid capturing the participant's face, while capturing the hand, arm, and object being gripped. All paper data with personally identifiable information including the consent forms and HIPPA forms will be stored in a key-locked cabinet in a key-locked room that is accessible to study personnel only. Other paper data without personally identifiable information including testing sheets documenting testing sequences and notes will also be stored in a cabinet in a key-locked room that is accessible to study personnel only.

Data sharing: Only de-identified coded data will be reported and/or shared with the public and other investigators

in publications, in ClinicalTrials.gov, or via data depository.

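### The primary repeated-measures ANOVA leaves covariance, post-hoc error term and missing data unspecified; in its conventional form the week-10 standard error can be too small, and a mixed model should replace it

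*Combined protocol and SAP*

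**What the plan says.** Section 10.0 (Analysis) gives one primary method: "The primary analysis will be a repeated measures ANOVA for each outcome". The response is a change score: "The dependent variables will be the change from baseline at the evaluation times". On model terms it says: "The primary independent variables are group, evaluation time, and their interaction"; sex and its interactions are added. The week-10 comparison is conditional: "If the group by time interaction is significant, we will examine if there is a group difference at 10 weeks using post-hoc tests".

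The Analysis paragraph is silent on covariance structure, sphericity, the error term of the post-hoc test and missing visits. The only covariance assumption in the document is in the sample-size paragraph, a "compound symmetry correlation of 0.92" taken from the pilot study. That paragraph also gives the 0.017 significance level and the 15% attrition. Section 12.0 permits the investigator to use data collected before withdrawal, but does not say how they enter the analysis.

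Section 9.0 gives two lists of evaluation times. One reads "Evaluation will be performed at baseline, after 2, 4, and 6 weeks of continuous task practices and at 1-month follow-up", which makes four change scores. The Schedule paragraph allots evaluation visits "for each of the 3 time points (baseline, after therapy, and follow-up"), which would make two.

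**The concern.** In its textbook form, a repeated-measures ANOVA pools the error over visits and needs every participant to have every visit. Change from a single baseline often becomes more variable as time from baseline grows. Here week 10 is the furthest visit and comes after the longest gap. A pooled error would average its variance with those of the earlier, less variable changes. A Greenhouse-Geisser correction repairs the interaction F test but leaves the week-10 standard error untouched.

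The sample size is justified by a difference at follow-up, so the week-10 contrast is the result readers will look to. At stake are the confidence interval and p-value for that contrast, the validity of the interaction test that precedes it, and the information from participants who leave early.

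**Working it through.** **1. Where the plan uses compound symmetry.** Inputs from Section 10.0: SD 5.1 s, difference 4 s, correlation 0.92, m = 4 time points, alpha 0.017 (sidedness not stated; two-sided reproduces the figure), power 80%.

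n per group = 2·SD²·(z₁₋α/₂ + z_power)²/δ² × [1 + (m−1)ρ]/m
= 2 × 26.01 × (2.387 + 0.842)²/16 × (1 + 3 × 0.92)/4
= 33.89 × 0.94 = 31.85, so 32. Then 32/0.85 = 37.6, so 38 per group, 76 in total.

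The stated figure reproduces. Compound symmetry serves the sample size here; nothing carries it into the Analysis paragraph.

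**2. Standard-error ratio.** Assume a constant raw-score SD and write ρ_t for the correlation of visit t with baseline. Then Var(change at t) = 2·SD²·(1 − ρ_t). The pooled error estimates the average of these variances over visits, so

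pooled SE / true week-10 SE = √(mean variance / week-10 variance).

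The SD cancels. The document does not say whether 5.1 s is a raw-score or change-score SD; treating it as raw only sets the scale below.

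- *Compound symmetry at 0.92:* every change SD is 5.1 × √0.16 = 2.04, and the ratio is 1.00.
- *Strong fading (assumed), 0.92 per 2 weeks:* change SDs 2.04, 2.83, 3.39, 4.21. Mean variance (4.16 + 7.99 + 11.51 + 17.73)/4 = 10.35, and √(10.35/17.73) = 0.76.
- *Mild fading (assumed), 0.95 × 0.985^(weeks/2):* change SDs 1.83, 2.02, 2.19, 2.49. Mean variance (3.34 + 4.07 + 4.79 + 6.20)/4 = 4.60, and √(4.60/6.20) = 0.86.

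**3. Rejection rates with no true effect.** 40,000 simulated trials per pattern, 32 per group, change scores at weeks 2, 4, 6 and 10, nominal 0.017, sex terms left out. Pooled error = (MS_between + 3·MS_within)/4 with Satterthwaite degrees of freedom. Simulation error near the nominal level is √(0.017 × 0.983/40,000), or 0.06 percentage points.

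| Assumed pattern | SE ratio | Interaction F | Week 10, pooled | Both (planned rule, pooled) | Week 10, own variance |
|---|---|---|---|---|---|
| Compound symmetry 0.92 | 1.00 | 1.8% | 1.7% | 0.2% | 1.7% |
| Very mild, 0.94 × 0.995^(weeks/2) | 0.94 | 1.8% | 2.6% | 0.3% | 1.8% |
| Mild | 0.86 | 2.0% | 3.9% | 0.7% | 1.7% |
| Strong, 0.92 per 2 weeks | 0.76 | 3.2% | 6.6% | 2.1% | 1.6% |
| Strong, mean correlation 0.92 | 0.75 | 3.6% | 7.2% | 2.5% | 1.8% |
| Change scores: correlation fades, equal variances | 1.00 | 3.3% | 1.7% | 0.2% | 1.8% |

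The last row shows that fading among the change scores is not enough by itself: the week-10 variance must exceed the average over visits. Greenhouse-Geisser brings the interaction test to between 1.5% and 2.0% in every row. Run at nominal 5%, the pooled week-10 test rejects 9.2% (mild) to 13.9% (strong), so a pooled 95% interval would cover about 91% to 86%.

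**4. Only weeks 6 and 10 analysed.** Under strong fading (0.92 per 2 weeks), √[((11.51 + 17.73)/2)/17.73] = 0.91. Simulated rates are: interaction 1.8%, pooled week 10 3.0%, both 0.4%.

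**5. Baseline adjustment.** At constant SD, the residual variance after baseline adjustment divided by the change-score variance is (1 − ρ²)/[2(1 − ρ)] = (1 + ρ)/2. That is 0.96 at ρ = 0.92, and 0.83 at the strong-fading week-10 value of 0.92⁵ = 0.66.

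**6. Missing visits.** The plan allows for 76 − 64 = 12 participants not completing. A complete-case ANOVA would use none of their post-baseline visits.

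**The case against.** The strongest reply is that the documents never state a pooled error. They say only that post-hoc tests follow the ANOVA, and a group comparison on week-10 data alone fits that wording and holds its level. This stands, and it is why the point is framed as non-specification plus the consequence of the conventional reading. It is not a full defence: an unstated error term can be chosen once the data are seen.

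Second, the fading patterns are assumptions. The only correlation evidence in the document is the pilot compound-symmetry value, under which nothing is inflated. This stands too, so the sizes are conditional.

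Third, a reader might infer that the trial's false-positive rate would be 4% to 7%. The documents do not support that. Those rates describe the week-10 test in isolation, whereas the plan runs it only after a significant interaction. The gate does not, however, correct a week-10 confidence interval built on a pooled error.

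Fourth, a reader might infer that data from participants who drop out will be discarded. Section 12.0 allows their use, so deletion is inferred from the name of the method. But permission to use data is not an analysis method, and none is given.

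Fifth, a week-10 test with its own variance plus a Greenhouse-Geisser correction would restore both error rates without a mixed model. That is true, but it would leave baseline adjustment and incomplete visits unaddressed.

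**Conclusion.** The point holds as a conditional weakness in the named primary method, not as a demonstrated error. Under the conventional reading, and only if the week-10 change is more variable than the average visit, the week-10 standard error is about 14% to 25% too small for mild to strong fading. The two-step rule then rejects about 0.7% to 2.5% against 1.7%, and only strong fading takes it above nominal. The mechanism disappears under compound symmetry or with a week-10-only post-hoc test, and shrinks if only weeks 6 and 10 enter.

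The lack of baseline adjustment and of a rule for incomplete visits does not depend on those correlation assumptions. The rates rest on normal data, 32 complete participants per group and no sex terms. The plan should be changed, because the gap is certain even though its size is not.

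**What to change.** Replace the ANOVA in Section 10.0 with a mixed model for repeated measures on all randomised participants, using every available post-baseline visit. Fixed effects: group, visit, group-by-visit, the baseline value of the outcome, and the sex terms already planned. Use an unstructured covariance over post-baseline visits and Kenward-Roger degrees of freedom. Take the week-10 group contrast from this model with its own standard error and confidence interval. State that incomplete participants are handled under a missing-at-random assumption.

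Reconcile the two lists of evaluation times in Section 9.0, and say whether the 4 time points in the sample-size paragraph include baseline. If the week-2 and week-4 evaluations take place within therapy sessions, say so.

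The cost is SAP wording and standard software. With four post-baseline visits, the unstructured matrix has 4 × 5/2 = 10 parameters against 2 for compound symmetry. Any loss of precision if compound symmetry holds was not computed.
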